After providing informed consent / assent, participants will be enrolled in the study. After completing a baseline survey, parent-adolescent pairs will be randomized to one of three groups: control (standard ED care), A-F texting component alone, or A-F in combination with P-F texting component. Parents randomized to either A-F or A-F plus P-F intervention groups will receive the text-based intervention over a course of six weeks following their adolescent's ED discharge. The P-F component includes an embedded MRT, which will allow us to examine the feasibility and acceptability of conducting an MRT, as well as explore if and under what conditions receiving the P-F message may be most beneficial. Participants who are randomized to receive the P-F texting component (as part of the A-F + P-F intervention arm) will be randomized twice each day (morning and evening) to either receive or not receive the P-F message at each randomization; at each randomization, the probability of either receiving or not receiving the P-F message will be 50%. As such, parents receiving the P-F component will receive between none and two P-F messages on any given day, on average receiving one P-F message on any given day. Over the course of the 6-week intervention, parents in the A-F condition will receive between 1-3 messages, based on randomization (on average, 2 messages each day).

Assessment Procedures for Aim 2:

Participating parents and adolescents will complete baseline assessment during the index ED visit. Parents and adolescents will be asked to complete baseline measures using Qualtrics on a study-provided tablet computer. Participants will also be provided the option of filling out the measures using a paper and pencil format if they prefer or if any technological difficulties are encountered that would

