prevent the completion of the surveys on a tablet computer. Parents and adolescents will each receive \$10 for completing the baseline assessment. Follow-up assessments will be conducted approximately 2, 6, and 12 weeks after enrollment. Parents and adolescents will complete assessments at 2 and 6 weeks using online surveys (using Qualtrics software). Parents will be compensated \$20, and adolescents will be compensated \$15 for completing each of the two online surveys. The 12-week follow-up, which will be used to assess youth suicide attempts and return ED visits, will be conducted over the telephone by a trained research interviewer. Adolescents and parents will each receive \$30 for completing the 12-week assessment. Chart data will also be abstracted to obtain relevant clinical information (e.g. psychiatric diagnoses, reason for hospitalization, previous hospitalizations). Finally, parent satisfaction with intervention components will also be assessed.

Aim 2 assessments were not collected for assessing primary or exploratory outcomes unless noted within the Aim 2 data analysis section.

Baseline Assessments

Parents at Baseline:

- Demographics
- DERS-SF
- Parental Self-Efficacy Scale
- PSC-17
- Mental Health Service Utilization Scale
- Multidimensional Scale of Perceived Social Support
- PHQ-4
- PHQ-10
- CGSQ-SF7
- Family History Screen
- GF-FAD
- Social/Emotional Support
- PANAS
- Munich Chronotype Questionnaire
- Safety measures (home environment lethal means restriction)

Adolescents at Baseline:

- Demographics
- DERS-SF
- AUDIT-C
- C-SSRS
- NIDA-modified ASSIST
- NSSI
- PHQ-9
- GAD-7
- Brief Hopelessness Scale
- Self-Efficacy to Cope with Suicidal Thoughts and Urges Scale
- Self-Rated Expectations of Risk
- Parent-Family Connectedness Scale
- GF-FAD
- Parent-Family Connected Scale
- Pediatric Family Relationships

Follow-Up Assessments at 2, 6 and 12 weeks

Parents:

- Parents' engagement in suicide prevention activities
- Parental Self-Efficacy Scale (parental coping self-efficacy)
- Social/Emotional Support
- PHQ-4 (depression and anxiety symptoms)
- PHQ-10 (areas of functioning in daily life)
- CGSQ-SF7 (caregiver stress)
- PANAS (positive and negative affect)
- Mental Health Service Utilization Scale (only at 6 and 12 weeks)
- Intervention Feedback (only at 6 weeks)
- Multidimensional Scale of Perceived Social Support (only at 12 weeks)

_

Adolescents:

- Parents' engagement in suicide prevention activities

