- PHQ-4 (depression and anxiety symptoms)
- PHQ-10 (areas of functioning in daily life)
- Brief Hopelessness Scale (hopelessness)
- Self-Efficacy to Cope with Suicidal Thoughts and Urges Scale (suicide coping self-efficacy)
- Self-Rated Expectations of Risk (perceived suicidal behavior risk)
- Parent-Family Connectedness Scale (perceived connectedness to parents/family)
- Pediatric Family Relationships (family support)
- Mental Health Service Utilization (only at 12 weeks)
- C-SSRS (only at 12 weeks)

Daily Surveys:

All parents will respond to brief daily surveys over the 6-week intervention. Two brief (1-2 min) online surveys will be sent to parents' phone each day (morning and afternoon/evening) via text message using a secure automated delivery system. Parents will be provided with approximately 2 hours to complete the daily survey. To increase adherence, parents will be provided with an incentive of \$2 for each daily survey. Items will be brief and drawn from known and validated scales.

Data Analysis for Aim 2:

Primary Analysis: We will obtain descriptive data related to intervention feasibility and acceptability as measured by: (1) percentage of eligible participants who agree to participate in the study, (2) percentage of participants who complete follow-up assessments, (3) of those randomized to the texting intervention, percentages of parents who remain active (i.e. do not request to stop receiving messages), and (4) parents' satisfaction with the intervention.

Exploratory Analyses: In exploratory analyses, we will explore the effect of intervention on the proposed mechanism of change (parental self-efficacy) assessed at 2-, 6-, and 12-weeks post enrollment, we will use multi-level analyses for continuous variables (linear mixed-effects models). We will also conduct exploratory analyses of the effect of intervention on the proposed distal outcome of parental engagement in supportive and suicide prevention activities, assessed at 2-, 6-, and 12-weeks post enrollment. Analyses will be conducted using an intent-to-treat approach. Finally, we will describe differences between intervention vs. control regarding youth suicidal behavior outcomes at the 12-week follow-up.

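### The exploratory self-efficacy model does not say whether it uses the baseline score that the trial already collects

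*Combined protocol and SAP*

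**What the plan says.** In Data Analysis for Aim 2, the Exploratory Analyses paragraph gives the outcome, visits and model for the proposed mechanism: "parental self-efficacy) assessed at 2-, 6-, and 12-weeks post enrollment, we will use multi-level analyses for continuous variables (linear mixed-effects models". It adds that analyses follow intention to treat. No baseline covariate or time-zero response is mentioned there or anywhere else.

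The baseline value exists:

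- The parents' baseline list includes the "Parental Self-Efficacy Scale".
- The parents' follow-up list for 2, 6 and 12 weeks repeats it: "Parental Self-Efficacy Scale (parental coping self-efficacy").
- The Overview of Aim 2 Procedures puts it before allocation: "After completing a baseline survey, parent-adolescent pairs will be randomized to one of three groups".

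Two features of measurement bear on how well baseline predicts follow-up. Under Assessment Procedures for Aim 2, "Participating parents and adolescents will complete baseline assessment during the index ED visit", and the 12-week follow-up "will be conducted over the telephone by a trained research interviewer", whereas weeks 2 and 6 use online surveys.

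The same section also says: "Aim 2 assessments were not collected for assessing primary or exploratory outcomes unless noted within the Aim 2 data analysis section". The Aim 2 analysis section mentions self-efficacy only at the three follow-up visits.

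**The concern.** As written, the model covers three post-randomisation scores and leaves out a pre-randomisation measurement of the same quantity. Read literally, the arm contrasts would carry between-parent variation that the baseline score could remove. In a small three-arm pilot that is wasted information about the one variable that the plan calls its mechanism.

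The silence also leaves a choice open. Ignoring baseline, adjusting for it, and analysing change from baseline give different estimates with different precision. If the choice is not fixed in advance, it can be made after the results are seen.

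The stakes are limited. The Methods section classes everything outside the Primary Analysis as exploratory or ancillary, the primary analysis is descriptive, and no stated power or precision target depends on this model.

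**Working it through.** The plan gives no sample size, power or precision figure for this analysis, so there is nothing to reproduce. The check asks how much the standard error of an arm difference changes when baseline is added.

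**Inputs from the documents:** three arms; follow-up at 2, 6 and 12 weeks; the same scale at baseline, before randomisation.

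**Inputs assumed, because the documents give none:** equal arms of n = 10, 20 or 30; baseline-to-follow-up correlation from 0 to 0.5; equal variances; complete follow-up; one normally distributed covariate.

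**Cost of estimating the slope.** With three arms the within-arm degrees of freedom are 3n - 3. Estimating one common baseline slope inflates the variance of an arm difference, on average, by

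f = 1 + 1/(3n - 5)

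- n = 10: 1 + 1/25 = 1.040
- n = 20: 1 + 1/55 = 1.018
- n = 30: 1 + 1/85 = 1.012

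**Single visit.** Ratio of adjusted to unadjusted standard error = sqrt((1 - rho²) × f). For example, with rho = 0.5 and n = 10, sqrt(0.75 × 1.040) = 0.883, a cut of 11.7%.

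| rho | n = 10 | n = 20 | n = 30 |
|---|---|---|---|
| 0 | +2.0% | +0.9% | +0.6% |
| 0.1 | +1.5% | +0.4% | +0.1% |
| 0.2 | -0.1% | -1.1% | -1.4% |
| 0.3 | -2.7% | -3.7% | -4.0% |
| 0.5 | -11.7% | -12.6% | -12.9% |

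**Break-even.** Setting (1 - rho²) × f = 1 gives rho = sqrt(1 - 1/f) = 0.196, 0.134 and 0.108 for n = 10, 20 and 30. Below these values adjustment costs a little; above them it gains.

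**Mean of the three visits.** Let b be the correlation of baseline with each follow-up and w the correlation between follow-ups. The mean has variance u = (1 + 2w)/3 and covariance b with baseline, so the ratio is sqrt(f × (u - b²)/u). For b = 0.3 and w = 0.6, u = 0.733, and at n = 10 the ratio is sqrt(1.040 × 0.643/0.733) = 0.955.

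| b, w | Cut before slope cost | n = 10 | n = 20 | n = 30 |
|---|---|---|---|---|
| 0.3, 0.6 | 6.3% | 4.5% | 5.5% | 5.8% |
| 0.5, 0.7 | 17.1% | 15.4% | 16.3% | 16.6% |
| 0.5, 0.5 | 20.9% | 19.4% | 20.2% | 20.5% |

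The last row is compound symmetry, the favourable case.

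**Simulation check** (20,000 replicates per setting, no treatment effect). Both estimators averaged within 0.005 SD of zero. Single-visit cuts at n = 10, 20, 30 were 2.7%, 3.5%, 3.9% for rho 0.3 and 11.5%, 12.5%, 12.9% for rho 0.5, close to the formula.

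**Change scores are not a substitute.** The variance of a change score is 2(1 - rho) and that of the adjusted score is 1 - rho², so their ratio is (1 + rho)/2: 0.65 at rho 0.3 and 0.75 at rho 0.5. A plain change-from-baseline contrast therefore does not deliver the gain above.

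**The case against.** The strongest reply is that this is silence and not a wrong choice. The paragraph is short. It also leaves random effects, time coding and contrasts unstated, and a linear mixed model can take baseline as a covariate or as a response. Precision is lost only if the team leaves baseline out, which the plan does not say it will do. That is fair, and it is why the point is graded as something to consider. It does not remove the point: the model as written covers only follow-up scores, and if adjustment is already intended, the remedy is the same sentence.

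Other objections stand in part:

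- The statement about which assessments serve outcomes concerns outcomes, not covariates. It does not forbid adjustment, and the case does not rest on it.
- Baseline is taken during a crisis visit and week 12 is by telephone, so the correlation could be weak. Below break-even, adjustment is a small net loss.
- The unadjusted contrast is unbiased with complete data or suitable missingness. If dropout depends on baseline self-efficacy and arm, it need not be. That is a further reason to include baseline, but it means that the figures, which assume complete follow-up, are illustrations.
- The size rests entirely on assumed inputs, and even its sign depends on the correlation.

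**Conclusion.** The point holds as a low-severity improvement. The plan does not say whether baseline self-efficacy enters the model, although the score is collected before randomisation on the same scale.

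The trade is lopsided. At the assumed 10 to 30 per arm, the worst case is a standard error about 2% larger (10 per arm, no correlation). At a correlation of 0.5, it is about 12% to 13% smaller at a single visit and about 15% to 20% smaller for the three-visit mean, depending on the correlation between follow-ups. Before the slope cost, a correlation of 0.5 cuts single-visit variance by 25%, equivalent to about a third more participants (1/0.75 = 1.33).

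Confidence in the exact gain is only medium, because neither arm size nor correlation is documented. No feasibility or acceptability conclusion changes.

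**What to change.** Add one sentence to the Exploratory Analyses paragraph, before analysis: the self-efficacy model includes the baseline Parental Self-Efficacy Scale score as a covariate. A constrained longitudinal model, with baseline in the outcome vector and a common baseline mean across arms, is an acceptable alternative; name one of the two. A baseline-by-visit term is optional. If the analysis has already been run, report which model was used and label any later adjustment as post hoc.

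The fix does not carry over to "parental engagement in supportive and suicide prevention activities, assessed at 2-, 6-, and 12-weeks post enrollment", because that measure is listed at follow-up but not at baseline. The parents' baseline list does contain a home lethal-means safety measure in a related domain, but it is not the same measure.

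The cost is one sentence, no new data and one degree of freedom for a single slope.

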Text messages offer an accessible continuity of care strategy after ED care, as they are nearly ubiquitous in the United States, ²² and have been used to support a range of behavioral and health outcomes. ²³⁻²⁷ Because suicidal adolescents are heterogeneous with respect to varying levels of suicide risk ^{33,34}—and parents may experience varying caregiving challenges and stress—a texting intervention should ideally be tailored to address parents' unique and changing needs. Aiming to maximize outcomes while minimizing burden, a Just-In-Time Adaptive Intervention (JITAI) is an intervention design that adapts the provision of mobile-based interventions to meet the dynamically changing needs of individuals in the "real" world. ^{35,36} This study will build the foundation for an effective JITAI for parents of suicidal youth by investigating the feasibility and acceptability of employing a microrandomized trial (MRT)—an experimental design used for optimizing JITAIs. ³⁸

STUDY PURPOSE

This study seeks to develop and pilot an adaptive, text-based intervention for parents of suicidal youth transitioning from ED care. The study will address an urgent need for efficacious continuity of care strategies for suicidal youth post ED care using a scalable approach. The study's aims are as follows:

Aim 1 (Non-Clinical Trial):

Finalize text-based intervention components in preparation for the pilot study. Drawing on theoretical and clinical considerations, as well as our preliminary parent focus group data, we will develop text messages focused on two domains: (1) messages encouraging parental provision of adolescent-focused (A-F) support (e.g., suicide prevention activities, communication, tips for supporting at-risk youth); and (2) messages providing parent-focused (P-F) support (e.g., affirmation, tips for parents' own well-being). Text messages will be iteratively refined based on input from experts and parents.

Aim 2:

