Unless listed in the Primary Analysis under "Data Analysis for Aim 2" section, all outcomes and assessments are exploratory or ancillary.

Aim 1 (Non-Clinical Trial) Methods:

Initial Development of Text Messages: An initial "bank" of text messages for the A-F and P-F intervention components will be developed using an iterative process. This process will draw on (a) relevant theory, (b) best-practice recommendations, (c) content area knowledge, and (d) our research team's preliminary data drawn from previous focus groups conducted with parents of suicidal adolescents after ED discharge. The tone of the messages will incorporate Motivational Interviewing (MI) principles as an additional strategy to increase parents' self-efficacy and motivation to implement the suggested recommendations and tips for adolescent- and parent-directed support. Some messages will incorporate links to additional online resources or information.

Description of Components and Sample Messages:

Adolescent-focused support (A-F component): The A-F texting component will include content consistent with best-practice recommendations for parents to buffer youth against suicide risk. This will incorporate messages focusing on: (1) restricting access to lethal means; (2) recognizing and attending to suicide warning signs; (3) encouraging adolescent's use of coping strategies; (4) ways parents can support and assist the youth in using the safety plan; (5) monitoring and supervising the youth with sensitive queries about mood and suicidality; (6) responding in a sensitive manner to disclosures of distress and suicidality; (7) tips for communication; (8) providing emotional support and engaging in activities promoting connectedness; and (9) reminders about crisis resources.

Parent-focused support (P-F component): The P-F texting component will include content focused on providing parent-directed support (e.g., encouragement, affirmations), as well as tips for parents' self-care and own well-being.

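### Parental engagement in suicide prevention activities has no listed baseline, and the baseline lethal-means measure has no listed repeat; this costs precision and change from baseline, not validity

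*Combined protocol and SAP*

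**What the plan says.** Under Data Analysis for Aim 2, Exploratory Analyses, the plan states: "We will also conduct exploratory analyses of the effect of intervention on the proposed distal outcome". The same sentence describes that outcome as the "proposed distal outcome of parental engagement in supportive and suicide prevention activities, assessed at 2-, 6-, and 12-weeks post enrollment". The sentence on the mechanism, parental self-efficacy, says "we will use multi-level analyses for continuous variables (linear mixed-effects models)". No model is named separately for engagement, and no baseline covariate is named for either outcome. Analysis is by intent to treat.

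Under Follow-Up Assessments at 2, 6 and 12 weeks, "Parents' engagement in suicide prevention activities" is listed for parents and for adolescents. It is on neither list under Baseline Assessments. The parent baseline list ends with "Safety measures (home environment lethal means restriction)", which is on no follow-up list.

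The intervention content overlaps with both measures. The study aims describe "messages encouraging parental provision of adolescent-focused (A-F) support (e.g., suicide prevention activities, communication, tips for supporting at-risk youth)". In Description of Components and Sample Messages, the first of nine adolescent-focused (A-F) topics is "1) restricting access to lethal means".

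On design, Overview of Aim 2 Procedures says that after the baseline survey "parent-adolescent pairs will be randomized to one of three groups: control (standard ED care), A-F texting component alone", or A-F combined with the parent-focused component. The primary analysis is descriptive feasibility and acceptability. Other outcomes are exploratory or ancillary.

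**The concern.** The named distal outcome of Aim 2a has follow-up without a baseline, while the most closely related baseline measure has no listed follow-up. As listed, no suicide prevention behavior of the parent is measured under the same name before and after the texts.

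In a three-arm pilot, arms can differ by chance in what parents already do. Without a baseline, that difference can be neither seen nor removed, and the intervals for the arm contrasts are wider than they need to be. A family that already did what the texts suggest also looks the same at follow-up as one that changed. A null result on engagement could then mean no effect or little room to improve. A family lost before week 2 contributes no engagement value at all.

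The gap looks more like an oversight than a principle, because the mechanism measure, the Parental Self-Efficacy Scale, is collected at baseline and at follow-up.

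**Working it through.** **1. Comparing the lists.** The plan states no sample size, power, standard deviation or correlation for this outcome, so there is no figure to reproduce. The main check is the schedule.

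| Measure | Baseline | 2, 6, 12 weeks |
|---|---|---|
| Engagement, parent report | not listed | listed |
| Engagement, adolescent report | not listed | listed |
| Home lethal-means restriction, parent | listed | not listed |
| Parental Self-Efficacy Scale | listed | listed |

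The parent follow-up list has ten entries. Eight are also on the parent baseline list. The other two are Intervention Feedback, which cannot have a baseline, and engagement.

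**2. Is the arm comparison biased?** The target is an effect of intervention between randomized groups. Randomization follows the baseline survey and there is a concurrent control. Differences in follow-up means therefore estimate that effect without bias, apart from dropout. Change between follow-up visits can also be estimated; change from baseline cannot.

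**3. Precision at one visit.** Let r be the correlation of a baseline covariate with follow-up engagement (assumed). Relative to a follow-up-only analysis, with variance set to 1:

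- baseline as covariate: 1 − r²
- change score: 2(1 − r)

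| r (assumed) | Variance, covariate | Reduction | Standard error factor | Variance, change score |
|---|---|---|---|---|
| 0.1 | 0.99 | 1% | 0.995 | 1.8 |
| 0.3 | 0.91 | 9% | 0.954 | 1.4 |
| 0.5 | 0.75 | 25% | 0.866 | 1.0 |
| 0.6 | 0.64 | 36% | 0.80 | 0.8 |

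Below r = 0.5 a change score is less precise than having no baseline, so any baseline value belongs in the model as a covariate.

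**4. The same result as numbers per arm.** For illustration, assume a standardized difference d = 0.5, two-sided 5% level and 80% power. Then n per arm = 2(1.96 + 0.84)²(1 − r²)/d² = 62.7 × (1 − r²). This gives 63 with no covariate, 63 at r = 0.1 (62.1 rounded up), 58 at 0.3, 48 at 0.5 and 41 at 0.6.

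**5. Mean of the three visits.** Assume the same correlation r between all four time points. The follow-up-only variance is (1 + 2r)/3 and the adjusted variance is (1 + 2r)/3 − r². At r = 0.3 these are 0.533 and 0.443 (ratio 0.831). At r = 0.5 they are 0.667 and 0.417 (ratio 0.625). The saving is larger than at a single visit, but only under that correlation pattern.

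**6. Chance imbalance.** With n per arm, the difference between two arms in mean baseline engagement has standard deviation √(2/n), in outcome standard deviations. Assuming 15 to 40 per arm, that is √(2/15) = 0.37 to √(2/40) = 0.22. It carries into the follow-up contrast multiplied by r: about 0.04 to 0.02 at r = 0.1, and 0.22 to 0.13 at r = 0.6. This is the same variance component that steps 3 and 4 remove, not an additional loss.

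**The case against.** A reader might infer that the trial cannot show whether the texts alter parents' behavior. The documents do not support that. The plan claims an effect of intervention, not change from baseline, and the randomized control supplies the comparison.

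A reader might also infer that homes already secured at the index visit go unidentified. They are identified, because the safety measure is taken before randomization. They can be compared across arms and used for adjustment. Nor can it be said that lethal-means restriction is never measured again. The items of the engagement measure are not given and may include it; this can be neither confirmed nor excluded. Its first place among nine topics is list order only, with no stated priority or delivery sequence. A ceiling on that one topic would not be a ceiling on the broader outcome.

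Three further objections have weight. The correlations are assumed. Some A-F behaviors, such as helping with a safety plan, may have no counterpart before the visit for some families, so a baseline version could correlate weakly; at r = 0.1 the saving is 1%. Each informant's baseline list already has 15 entries, completed during an emergency visit. Participation and follow-up completion are themselves primary outcomes that added burden could affect.

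These points limit the claim and make a new baseline engagement measure optional. They do not answer the gap in the lists, and they do not weigh against using as a covariate a baseline measure that is already collected.

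**Conclusion.** The point holds as a gap in measurement and efficiency for an exploratory outcome. From the lists alone, engagement has no baseline from either informant, and the lethal-means measure has no listed repeat. Change from baseline in engagement therefore cannot be estimated, and chance imbalance in prior engagement cannot be checked or adjusted for. The between-arm comparison remains unbiased apart from dropout.

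The loss of precision depends on an unknown correlation. Over an assumed range of 0.1 to 0.6, it is 1% to 36% of single-visit residual variance, or about 0.5% to 20% of the standard error. If the covariate is the lethal-means measure rather than prior engagement, the relevant correlation is that measure's own with follow-up engagement, and the gain may be small. Whether lethal-means restriction lacks a follow-up measure altogether depends on items the documents do not show. The primary feasibility and acceptability analysis is unaffected.

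**What to change.** 1. Repeat the baseline lethal-means safety measure for parents in all arms in the online surveys at 2 and 6 weeks and the telephone assessment at 12 weeks, unless the engagement measure already contains the same items. In either case, state whether it covers lethal means.
2. Name the baseline safety measure as a covariate in the engagement model, for both parent and adolescent reports. It is collected before randomization and needs no new data. Specify it before outcome data are examined by arm.
3. Optionally, if survey burden in the emergency department allows, add to the pre-randomization baseline survey the few engagement items that apply before the visit, with a look-back ending at the visit. Use that score as the covariate, not in a change score. If this is not done, state that the engagement comparison uses follow-up values only.

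The cost is a few items in existing assessments and one model term, with no extra visit. The downsides are slightly longer surveys and possibly little gain in precision if the covariate is only weakly related to engagement.
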